**4.2 Study Schema**

The study schema is provided in Figure 3.

**Figure 3. Study Schema**

**4.3 Recruitment and Retention**

**4.3.1 Recruitment.** Potential participants will be recruited through various methods, which include but are not limited to advertisements, flyers, and word-of-mouth. Potential candidates will complete a pre-screen assessment and those who are potentially eligible and interested will be invited to sign informed consent and complete screening/baseline.

**4.3.2 Retention.** Strategies to maximize retention will include reminder phone calls prior to scheduled appointments and follow-up phone calls and, if needed, certified letters to participants missing a visit. Participants will also be

reimbursed up to \$220 for their time and travel. Peer Interventionists will be provided with a study cell phone for use in delivering TTIP-PRO and for staying in contact with research staff regarding scheduled and completed interventions. Peer Interventionists will be compensated \$40 for completing training/certification, and \$20 for each participant for whom they provide the intervention.

## 5.0 Data Storage and Analysis

### 5.1 Data Storage and Confidentiality

To maintain participant confidentiality, study records and data will be stored in compliance with the International Conference on Harmonization (ICH) guidelines. Participant records will be held confidential by the use of study codes in the study database, secure storage of any documents that have participant identifiers, and secure computing procedures for entering and transferring electronic data. No identifying information will be disclosed in reports, publications or presentations. Information collected for this study will be kept in a locked secure location accessible only to research staff and authorized personnel directly involved with this study.

### 5.2 Data Analysis

All analyses will be completed on the ITT sample using SAS (SAS Institute, Inc.). Statistical tests will be conducted at a 5% Type I error rate (two-sided) for all measures. It has been recommended that effect sizes be provided rather than using the Bonferroni procedure to adjust for multiple-comparisons; thus, effect sizes and 95% confidence intervals (CI's) will be computed for each treatment effect. For each efficacy analysis, demographic/baseline characteristics and length of time since last OOD will be selected for inclusion in the model using the corrected Akaike Information Criterion (AICC) as the optimizing criterion. For missing data, multiple imputation methods will be used and the resulting model compared to the non-imputed model. **Participant Analyses**-The primary hypothesis, that a significantly greater proportion of TTIP-PRO, relative to control, participants will enter MAT within 12-month follow-up will be tested using a logistic regression (a generalized linear model with a logistic link). Secondary analyses. The key secondary hypothesis, that a significantly lower proportion of TTIP-PRO, relative to control, participants will have a recurring OOD within 12-month follow-up will be tested using a logistic regression (a generalized linear model with a logistic link). The secondary hypothesis that TTIP-PRO, relative to control, participants will have a significantly greater reduction in illicit opioid use will be tested using two outcomes, one based on self-report and the other on UDS results. The proportion of self-reported use days will be treated as a binomial variable and regressed using logistic mixed model regression (random-intercept generalized mixed-model regression with a logistic link function). UDS results (positive for illicit opioids vs. not positive), will be treated as a binary variable which will also be regressed using logistic mixed-model regression. For both outcomes, the effects of interest will be treatment and treatment-by-time interaction.

Power: A pilot study necessitates a limited sample size, and is more useful for showing feasibility than providing an effect size estimate. The proportion of patients who will enroll in a MAT program is unknown for both the TTIP-PRO and control group. Thus, we based the estimated proportions on a recent randomized trial comparing buprenorphine administration during medical hospitalization and linkage to office-based buprenorphine post-discharge to buprenorphine detoxification. In that study, the linkage patients were more likely to enter office-based buprenorphine treatment (72.2%) compared to the detox group (11.9%). The linkage condition was much more intensive than TTIP-PRO and, thus, it is expected that the TTIP-PRO enrollment rate will be considerably less than that observed for the linkage group. Assuming that 12% of our control group enrolls in MAT, and a total sample size of 80, we would have 80% power using a two-tailed test and  $\alpha = .05$  to detect a TTIP-PRO effect for a MAT enrollment rate of  $\geq 39\%$ . In our SBIRT trial, our 12-month follow-up rate was 78%. If 78% of participants complete the 12-month follow-up ( $n=62$ ) in the proposed trial, we would have 80% power (assuming 12% engagement for the control group, a two-tailed test, and  $\alpha = .05$ ) to detect a TTIP-PRO effect for a MAT enrollment rate of  $\geq 46\%$ .

**Peer Interventionist Analyses** - The hypotheses related to the Peer Interventionists will be tested with descriptive statistics. The proportion of Peer Interventionists: 1) attending the training who complete training and certification within the expected 4-hour timeframe and 2) who report being satisfied or very satisfied with their experience as a Peer Interventionist will be calculated.

**Analyses for Exploratory Aims-** E1 – Testing the validity of the HOPI and PORS. The HOPI was designed to include two subscales (i.e., personally relevant; credible). Factor analyses will be used to determine if the HOPI does, in fact, yield two factors corresponding to the intended subscales. Since the HOPI uses Likert-scale variables, the factor analysis will be based on polychoric correlation. A logistic generalized linear model regression will be used to test the PORS score as a predictor of 1 year OOD rates. The strength of predictive validity will be expressed both as the estimated odds ratio and by area under a ROC curve.

E2 – Testing the conceptual model of TTIP-PRO’s mechanisms of change. The purpose of the analyses described here is to explore the degree to which our conceptual model is consistent with the obtained study results. Using all ITT data, we will perform mediation analysis (empirically estimating 95% confidence intervals via bootstrapping) to test three mediation relationships: 1. fear-of-treatment, expected-success, and desire-to-quit as joint mediators of the effect of TTIP-PRO on engagement-in-MAT, 2. desire-to-quit, expected-success, and engagement-in-MAT as joint mediators of the effect of TTIP-PRO on level-of-opioid-use, and 3. knowledge-of-opioid-overdose and level-of-opioid-use as joint mediators of the effect of TTIP-PRO on whether there is an opioid overdose recurrence. We will test whether helpfulness-of-the-intervention (HOPI) respectively moderates the effects of fear-of-treatment, expected-success, desire-to-quit, and knowledge-of-opioid-overdose. We will perform logistic regression when engagement-in-MAT and overdose-recurrence are outcomes and logistic mixed-model regression when opioid use is the outcome.

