### **1.5 Randomization Plan**

Eligible participants will be randomized in a 1:1 ratio to the control or experimental arms. The randomization sequence will be unknown to the research staff.

[figure not shown]

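### Agreement between multiple imputation and the non-imputed model cannot be relied on to detect outcome-dependent loss to follow-up that differs by arm, and no other missing-data check is planned

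*Combined protocol and SAP*

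**What the plan says.** The whole missing-data plan is one sentence in section 5.2 Data Analysis, repeated in section III.3 of the DSMP: "For missing data, multiple imputation methods will be used and the resulting model compared to the non-imputed model". No imputation model, list of imputation variables or missingness assumption is given. No delta-adjusted, tipping-point or worst-case analysis appears anywhere.

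The surrounding facts that matter here are:

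- **Testing.** "Statistical tests will be conducted at a 5% Type I error rate (two-sided) for all measures", on the ITT sample, with logistic regression for MAT entry (primary) and for recurrent overdose (key secondary).
- **Covariates.** Section 5.2 names demographic and baseline characteristics and time since last overdose, selected by AICC.
- **Expected loss.** The power paragraph contains a scenario that begins "If 78% of participants complete the 12-month follow-up" and gives n = 62. The rate is borrowed from another trial by the same team.
- **Outcome sources.** Section 1.4.1 bases MAT entry on the participant's report, with clinic records as confirmation, and bases overdose on the participant's report.
- **Interim data.** Table 1 tracks both outcomes at months 3, 6 and 12. DSMP III.2 says that treatment and overdose tracking involves transcription from medical records.

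**The concern.** The comparison looks like a robustness check, but its inputs are observed data only. Standard multiple imputation fills each gap by assuming that the missing participant resembles observed participants with the same values of the imputation variables. The complete-case logistic model makes a closely related assumption. If only a single Yes/No outcome is missing and it is imputed from arm and the analysis covariates, the two fits target the same coefficient and differ by little more than simulation noise. They will then agree whether or not the people who left differ from those who stayed.

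Loss related to the outcome, and differently so by arm, is conceivable here. TTIP-PRO participants are directed to a UC ASD MAT program whose clinic staff are co-located with the research team, while controls receive a list of local providers. TTIP-PRO entrants may therefore be easier to trace than control entrants. This is an inference from the design; the documents give no dropout rates by outcome. If it happened, both models would carry the same bias, and their agreement could give false comfort about a result intended to support a larger trial.

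**Working it through.** **1. The plan's own figures.** 80 × 0.78 = 62.4, so n = 62 reproduces, leaving 80 − 62 = 18 without a 12-month visit (about 9 per arm if equal). The stated 80% power also reproduces: 80.3% for 12% vs 39% at 40 per arm (pooled normal approximation), and 80.5% for 12% vs 46% at 31 per arm (Fisher's exact test). No single method gives both, but this point does not depend on that.

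**2. Size of the bias.** Let *e* and *f* be the fractions lost among events and non-events in an arm. With no true effect, the complete-case odds ratio tends to

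[(1 − e_T)/(1 − f_T)] ÷ [(1 − e_C)/(1 − f_C)],

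whatever the event rate. The loss rates below are assumptions.

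- Pattern A, control 40%/15.7%, TTIP-PRO 4%/28%: (0.96/0.72) ÷ (0.60/0.843) = 1.333 ÷ 0.712 = 1.87.
- Pattern B, control 58%/10%, TTIP-PRO 0%/29.3%: (1/0.707) ÷ (0.42/0.90) = 1.414 ÷ 0.467 = 3.03.
- The same pattern in both arms: the ratio is 1, so there is no bias.

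At a 25% event rate each pattern loses about 22% per arm; for A, control 0.25 × 0.40 + 0.75 × 0.157 = 0.218 and TTIP-PRO 0.25 × 0.04 + 0.75 × 0.28 = 0.22.

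**3. Does the planned check notice?** Simulation: 40 per arm, no true effect, 25% event rate, one baseline covariate, imputation from arm and covariate, 50 imputations, Rubin's rules, 1,500 trials per row.

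| Loss | Same significance call | Median gap, log OR | OR in both analyses |
|---|---|---|---|
| Ignorable, 22% | 99.1% | 0.03 | no bias |
| Pattern A | 98.3% | 0.03 | about 1.9 |
| Pattern B | 97.0% | not recorded | about 3.1 |

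A separate simulation with other loss rates (29% of TTIP-PRO non-entrants and 50% of control entrants lost) gave 95.7% agreement and a gap of 0.05, against 98.7% and 0.04 under random loss. Median log OR was 0.93 non-imputed and 0.91 imputed. False positives were 24.9% in both, against 4.0% with full data.

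**4. Dependence on the event rate.** The plan's control rate comes from "Assuming that 12% of our control group enrolls in MAT, and a total sample size of 80". False positives, no true effect:

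| | 25% event rate | 12% event rate |
|---|---|---|
| Full data | about 4.5% | about 2% |
| Pattern A | about 16–18% | about 5% |
| Pattern B | about 35–37% | about 10% |

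**5. If interim status is used.** Assume a binary interim status known for everyone, with 60% entry if present and 10% if absent. Median log OR, true value 0:

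| Loss depends on | Non-imputed | MI without interim | MI with interim |
|---|---|---|---|
| interim status | 0.56 | 0.55 | 0.06 |
| the outcome itself | 0.96 | 0.94 | 0.68 |

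In the second row, imputation with interim status still gave 19.8% false positives, against 5.3% with full data.

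**6. How few participants matter.** Take 4/31 vs 14/31 among completers, close to the plan's 12% vs 46%, with 9 missing per arm (assumed). Use z = (p_T − p_C)/√[p(1 − p)(2/n)], with p pooled.

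- Completers: 0.3226/√(0.2903 × 0.7097 × 2/31) = 2.80, p = 0.005.
- Missing filled at the observed arm rates, 5/40 vs 18/40: p = 0.001. This treats filled values as observed, so it overstates precision.
- All missing counted as not entered, 4/40 vs 14/40: p = 0.007.
- None of the 9 missing TTIP-PRO participants and 3 of the 9 missing controls entered, 7/40 vs 14/40: 0.175/√(0.2625 × 0.7375 × 2/40) = 1.78, p = 0.075.
- All 9 missing controls and no missing TTIP-PRO participants entered, 13/40 vs 14/40: p = 0.81.

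**The case against.** The strongest reply is that the imputation model is left open. Month-3 and month-6 tracking could enter it, and step 5 shows that the two analyses can then diverge sharply. This stands. A reader might infer that the check can never reveal informative loss, and the documents do not support that. What remains is that the plan does not commit to using interim data, and that even a strong interim variable removed only part of the outcome-dependent bias.

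Second, the loss patterns are invented and sharply opposed between arms. That also stands: equal outcome-dependent loss in both arms does not bias the odds ratio. A reader might take the 16–37% false-positive rates as this trial's risk. They need a 25% event rate; at the plan's 12%, pattern A gives about the nominal 5%, although the odds-ratio bias remains.

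Third, 18 missing outcomes should not be read as a forecast. The 78% is conditional and borrowed. A Yes at month 3 or 6 is already known, and medical records may fill further gaps. The documents do not, however, say that records replace missing self-reports.

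Fourth, the plan says only that the models will be compared. It does not say that agreement will be offered as proof of robustness, and no such intent should be read into it.

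Finally, this is a pilot that puts feasibility ahead of effect estimation. That limits the severity, but the primary hypothesis is still tested at two-sided 5%.

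**Conclusion.** The point holds in limited form. The only planned missing-data check compares two analyses that share missing-at-random type assumptions, so their agreement cannot be relied on to detect outcome-dependent loss that differs by arm. If imputation uses only arm and the model covariates, the significance calls match in about 96–99% of simulated trials, with a log odds ratio gap of 0.03 to 0.05, whether or not loss created the effect. With interim MAT and overdose status in the imputation, the check can expose loss explained by those data, but outcome-dependent loss only in part.

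The odds-ratio bias of about 1.9 or 3, and every false-positive figure, rest on loss rates that are not in the documents. They show what the check could miss, not what will happen. The better-supported facts are the absence of any analysis that varies the missing outcomes, the scenario of up to about 18 missing 12-month visits, and how few changed outcomes can alter the conclusion: three controls, together with no TTIP-PRO entrants among the missing, in the worked example.

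**What to change.** In section 5.2 and DSMP III.3:

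1. Keep multiple imputation and keep the non-imputed comparison, which can expose loss explained by interim data.
2. Include month-3 and month-6 MAT entry and overdose status in the imputation model.
3. Add a delta-adjusted (tipping-point) analysis for MAT entry and for overdose, with shifts set separately by arm over a prespecified grid, for example −2 to +2 on the log-odds scale, including opposite signs in the two arms.
4. Report the treatment effect and 95% CI across the grid and the smallest shift that changes the conclusion, with a comment on whether that shift is plausible.
5. State that agreement between the imputed and non-imputed models will not be presented as evidence of robustness to informative dropout.

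A single analysis counting all missing participants as not entered would not be enough: in the second simulation of step 3 it gave 27.1% false positives.

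The cost is brief text in two places and some extra SAS runs on data already being collected. The downside is that the result may be shown to depend on assumptions about unobserved participants.

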Individuals experiencing a non-fatal OOD are at heightened risk for future OODs. A recent study revealed that 7% of all patients who were treated for an OOD in an ED were treated for more than one OOD within a single year. The proportion of patients with more than one OOD was higher in particular subsamples, with 31% of Medicare and 25% of Medicaid OOD patients having more than one OOD ED visit in one year. Patients with repeated OODs accounted for 15% of all OOD ED visits and were more likely to be hospitalized. Attempts to mitigate OOD deaths have largely focused on naloxone, an opioid antagonist that is effective in OOD reversal. Specifically, there have been concerted efforts to increase the accessibility of naloxone and to train opioid-abusing individuals and their families on the signs of OOD and naloxone administration. Although naloxone can reverse an acute overdose there is no guarantee that it will be available in time. The only completely effective method for preventing subsequent OOD is successful treatment of the underlying opioid use disorder (OUD). Receiving medication assisted treatment (MAT) for OUD (e.g., methadone- or buprenorphine-maintenance) significantly reduces the likelihood of OOD. However, in addition to the barriers of waiting lists and the costs of MAT, inaccurate perceptions of MAT – including myths about its side effects and lack of efficacy – also prevent some individuals with OUD from entering treatment. Currently there are no published secondary prevention interventions to help patients who have experienced a non-fatal OOD enter OUD treatment.

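### The plan tests MAT entry and recurrent overdose by logistic regression with no method for sparse events; the main risk is to the key secondary endpoint if overdoses are as rare as the cited 7%

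*Combined protocol and SAP*

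**What the plan says.** Section 5.2 (Data Analysis) sets one error rate for everything: "Statistical tests will be conducted at a 5% Type I error rate (two-sided) for all measures". In place of a multiplicity adjustment, it promises an effect size and 95% confidence interval for every treatment effect.

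For the primary hypothesis, the text says that a greater proportion of TTIP-PRO participants "will enter MAT within 12-month follow-up will be tested using a logistic regression (a generalized linear model with a logistic link"). The key secondary hypothesis has the same form: a lower proportion of TTIP-PRO "participants will have a recurring OOD within 12-month follow-up will be tested using a logistic regression".

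Three further statements shape the model:
- Population and software: "All analyses will be completed on the ITT sample using SAS".
- Covariates: baseline characteristics and time since last overdose "will be selected for inclusion in the model using the corrected Akaike Information Criterion (AICC) as the optimizing criterion". The candidates are not listed.
- Missing data: "multiple imputation methods will be used and the resulting model compared to the non-imputed model".

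The data analysis plan in Appendix B, section III.3, repeats this text. Neither place says whether the test is Wald, likelihood ratio (LR) or score, or provides an exact, penalised or other method for sparse data.

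**The concern.** Read in the ordinary way, logistic regression means maximum likelihood with large-sample tests. With 40 participants per arm, or 31 per arm at the planned 78% follow-up, a rare outcome leaves very few events. Two things can then go wrong.

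First, the usual tests drift from 5% in opposite directions: Wald becomes conservative and LR liberal. As the plan names neither, two analysts following it faithfully could reach different conclusions from the same data.

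Second, if one arm has no events, the maximum-likelihood odds ratio is zero or infinite. Its Wald interval is then useless. The plan relies on effect sizes and intervals for interpretation, so it could have nothing to report for overdose.

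**Working it through.** **Inputs**
- Section 5.2, Power: "Assuming that 12% of our control group enrolls in MAT, and a total sample size of 80"; detectable TTIP-PRO rate 39% at N=80 and 46% at n=62 (78% follow-up); 80% power; two-sided 0.05.
- Section 1.5: 1:1 allocation, so 40 or 31 per arm.
- Background: "7% of all patients who were treated for an OOD in an ED were treated for more than one OOD within a single year"; 25% for Medicaid and 31% for Medicare patients. These are literature figures, not planning assumptions.

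**The plan's own figure.** Pooled two-proportion formula: power = Φ{[|p1−p2|√n − 1.96√(2p̄(1−p̄))] / √(p1(1−p1)+p2(1−p2))}. With n=40, p1=0.12, p2=0.39 and p̄=0.255, this is Φ[(1.708 − 1.208)/0.586] = Φ(0.852) = 0.803. The 39% reproduces. For 12% vs 46% at 31 per arm the same formula gives 0.857. Fisher's exact test gives 0.805, so the 46% matches Fisher. The two figures do not come from one formula.

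**Expected events under no effect**
- MAT at 12%: 80×0.12 = 9.6; 62×0.12 = 7.4.
- Overdose at 7%: 80×0.07 = 5.6; 62×0.07 = 4.3.
- Overdose at 25–31%: from 62×0.25 = 15.5 to 80×0.31 = 24.8.

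**True size.** Every 2×2 table (a, b events out of n per arm) was enumerated with binomial weights. The probabilities of tables whose statistic exceeds 3.84 were summed. A zero-event arm counts as no Wald rejection. The model is unadjusted. Firth means the penalised LR test. The last column is the probability of at least one arm with no events, 1 − [1−(1−pC)^n][1−(1−pT)^n].

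| Rate, both arms | n per arm | Wald % | LR % | Score % | Firth % | Zero-event arm % |
|---|---|---|---|---|---|---|
| 7% | 40 | 0.28 | 8.12 | 5.58 | 4.32 | 10.7 |
| 7% | 31 | 0.25 | 8.82 | 4.55 | 3.86 | 20.0 |
| 12% | 40 | 2.05 | 5.85 | 5.67 | 4.69 | 1.2 |
| 12% | 31 | 1.56 | 6.66 | 5.57 | 4.12 | 3.8 |
| 25% | 40 | 4.68 | 5.35 | 5.00 | 5.00 | <0.1 |
| 25% | 31 | 4.09 | 5.66 | 5.05 | 5.01 | <0.1 |
| 31% | 40 | 4.78 | 5.38 | 4.82 | 4.82 | <0.1 |
| 31% | 31 | 4.35 | 5.11 | 4.99 | 4.98 | <0.1 |

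**Zero-event arm in numbers.** At 7% and n=40, 0.93^40 = 0.055, so 1 − 0.945² = 0.107. At n=31, 0.93^31 = 0.105, so 1 − 0.895² = 0.200. If one arm's rate is halved to 3.5% (an assumption; no overdose effect is planned), the results are 1 − 0.945×0.760 = 0.282 and 1 − 0.895×0.669 = 0.402. At 25% vs 12.5% they are only 0.5% and 1.6%.

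**One table as illustration.** Three overdoses vs none, 31 per arm. The maximised log-likelihood is 3 ln(3/31) + 28 ln(28/31) = −9.856. Under a common rate it is 3 ln(3/62) + 59 ln(59/62) = −12.012. LR = 2×2.156 = 4.31, above 3.84, so LR rejects. Wald has no finite estimate to test.

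**Primary power in the plan's two scenarios** (exact, unadjusted)

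| Scenario | Wald | LR | Firth |
|---|---|---|---|
| 12% vs 39%, 40 per arm | 80.2% | 82.3% | 81.6% |
| 12% vs 46%, 31 per arm | 83.3% | 87.5% | 86.9% |

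**Covariate selection.** A simulation (1,000 runs, five assumed null covariates selected by AICC, Monte Carlo standard error about 0.7 points) gave these sizes:

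| Setting | Wald % | LR % | Firth % |
|---|---|---|---|
| N=80, 12% | 3.5 | 7.7 | 6.1 |
| n=62, 12% | 2.7 | 8.4 | 5.1 |
| n=62, 7% | 0.6 | 13.2 | 4.0 |

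**The case against.** The case on the other side has several sound parts.

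- **The test is not named.** The failings of Wald and LR are therefore conditional on an analyst's choice. The score test stays between 4.6% and 5.7% at 7% and 12%. This stands: the defect is an unspecified choice, not logistic regression as such. A score test still supplies no finite odds ratio when an arm is empty.
- **7% may be too low for this trial.** It describes repeat emergency-department treatment among all overdose patients. The trial enrols people with a recent overdose, a high-risk ASSIST score and an opioid-positive urine screen who are not in treatment, and it counts any self-reported overdose. At 25–31% the problem nearly disappears. This stands, but the plan states no rate, so the method should work across the cited range.
- **The enumeration is not the planned model.** It ignores covariates and imputation, and 31 per arm describes only the non-imputed comparison. This stands as a limit on precision. In the simulation, selection raised LR size further.
- **This is a pilot.** The plan calls it more useful for feasibility than for an effect size. It nevertheless specifies significance tests at 5%.

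A reader might infer that the primary loses its stated power. Wald power is 66% (Firth 71%) for 12% vs 39% at 31 per arm, but the plan pairs 39% with N=80 and 46% with n=62. In both of those, Wald exceeds 80%.

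**Conclusion.** The gap is real, and its size depends on the event rate. For the key secondary endpoint at 7%, Wald almost never rejects (0.3%) and LR rejects too often (8.1–8.8%). There is no finite odds ratio in 11–20% of trials with no effect, or 28–40% if one arm's rate is halved. For the primary at 12%, the effect is modest: Wald about 2%, LR 5.9–6.7%, score near 5.6%. No loss of the stated power is claimed.

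A reader might go further and infer that the error rate fails at any count up to about 20 events. The documents do not support that. About 20 MAT events (40×0.12 + 40×0.39 = 20.4) is the count when TTIP-PRO works, where type I error does not apply. With 20 events under no effect, Wald is 4.7% and LR 5.35%. Nor do they show that the overdose odds ratio will probably be inestimable, because 7% is a background figure beside 25–31%.

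The conclusion assumes maximum-likelihood fitting, equal arms and no covariates. The 3.5% rate and the five covariates are assumptions.

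**What to change.** In section 5.2 and in Appendix B, section III.3, state that MAT entry and recurrent overdose will be fitted by Firth penalised logistic regression (the FIRTH option in PROC LOGISTIC). State also that treatment will be tested by the penalised likelihood-ratio test and reported with profile-likelihood 95% confidence intervals. The test must be named, because choosing the Firth estimator alone leaves it open.

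The estimate is then always finite. Unadjusted size is 3.9–5.0% across rates of 7–31%, and power is 81.6% and 86.9% in the plan's two scenarios.

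The cost is a few lines of text, one SAS option and somewhat more programming to pool profile-likelihood results over imputed data sets. Size with AICC-selected covariates may differ somewhat from the unadjusted figures (4.0–6.1% in the simulation above). A standardised risk difference beside the odds ratio is optional; it would match hypotheses stated as proportions.
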